1.12 INCLUSION OF VULNERABLE PARTICIPANTS

This study will involve recruitment of adolescents age 12-<21 years as the aim of the clinical trial is to determine the efficacy of liraglutide to promote weight loss in adolescent patients, a population with limited medical treatment options for moderate to severe obesity. The study will not involve recruitment of other vulnerable populations including pregnant women, prisoners, NIH employees, adults who lack consent capacity, including the mentally ill, and cognitively impaired participants because they do not meet the inclusion criteria for this study.

1.13 INCLUSION OF PREGNANT WOMEN, FETUSES OR NEONATES

Not Applicable

1.14 LIFESTYLE CONSIDERATIONS

Not Applicable

1.15 SCREEN FAILURES

Screen failures are defined as participants who consent to participate in the clinical trial but are not subsequently assigned to the study intervention or entered in the study. A minimal set of

Abbreviated Title: Liraglutide in Teens Post-SG

Version Date: 1/30/23

screen failure information is required to ensure transparent reporting of screen failure participants, to meet the Consolidated Standards of Reporting Trials (CONSORT) publishing requirements and to respond to queries from regulatory authorities. Minimal information includes demography, screen failure details, eligibility criteria, and any serious adverse event (SAE).

Individuals who do not meet the criteria for participation in this trial (screen failure) because of use of weight loss medication like phentermine, topiramate, lisdexamfetamine, orlistat, and naltrexone HCl/bupropion HCl may be rescreened three months after discontinuing the medication. Rescreened participants should be assigned the same participant number as for the initial screening.

1.16 STRATEGIES FOR RECRUITMENT AND RETENTION

Recruitment: A total of at most 50 participants to be screened at the NIH for protocol participation will be recruited from Washington, DC and local suburbs in Maryland and Virginia, with expected accrual rate of approximately 4 participants per month. Recruitment efforts will aim to enroll subjects in proportion to their representation in the population of Maryland. Subjects of all racial, ethnic and socio-economic backgrounds will be invited to participate in this study. Tools used for the recruitment of subjects will include the posting of the study description on the NIH Clinical Trials website. Additionally, flyers will be placed on bulletin boards at different buildings throughout the NIH campus and CNH. Recruitment material will be IRB approved prior to dissemination. Potential participants may also be referred by local providers responsible for clinical care. This includes providers from CNH's Bariatric Surgery Clinic and CNH's Obesity Program (multidisciplinary IDEAL Clinic) as well as from other community providers to whom we will provide our study information via a physician mailing letter and recruitment flyer. If necessary, further subjects will be recruited through newspaper advertisements or letter mailings. Advertisements will be submitted to the IRB before use.

Retention: There are incentives for attendance at study visits in terms of compensation for the time spent for, and inconvenience of, participation (see Compensation). We have a well-established track record of success in retaining participants with obesity for pharmacotherapy trials in adults and children [56-60]. For example, we recruited 340 adults for a 2-year pharmacotherapy RCT, retaining 82% for 1-year and 75% for 2-year study outcome measurements.

1.16.1 Costs

The trial drug will be provided at no cost to the patient. All trial related testing will be performed at no cost to the patient.

1.16.2 Compensation

Enrolled participants will be financially compensated for participation in this study for attending study visits as follows:

Compensation per visit- to be given at the end of each visit

1. Outpatient screening visit:	\$50
2. Baseline evaluation visit:	\$200
3. Interim Safety Visits (three total @\$25 per visit):	\$75

Abbreviated Title: Liraglutide in Teens Post-SG

Version Date: 1/30/23

4. Visit 5	\$200
5. Optional stool samples (up to 2 @\$25 per sample)	\$50
6. Final Visit:	\$50
Total=	\$575 to \$625

Compensation per procedure at Baseline evaluation visit:

1. History and Physical Exam	\$20.00
2. OGTT	\$50.00
3. DXA	\$30.00
4. Accelerometer	\$20.00
5. Blood draw	\$30.00
6. Questionnaires	\$50.00
7. Optional Stool Collection	\$25.00
Total	\$200 to \$225.00

The participants will be compensated for the parts of the study that they have completed. Payments will be sent after the visit either by check or direct deposit. If the participant is a minor, the guardian will receive the visit payment on behalf of the minor subject.

Guardians accompanying minors to NIH will be compensated \$40 per visit x 7 visits: \$280 which will be paid as a lump sum at the completion of the study.

Travel expenses (mileage, Metro, or taxi fare) will also be reimbursed per NICHD guidelines.

STUDY INTERVENTION

1.17 STUDY INTERVENTIONS(S) ADMINISTRATION

1.17.1 Study Intervention Description

The following description is quoted from the FDA-approved package insert [61]: “SAXENDA contains liraglutide, an analog of human GLP-1 and acts as a GLP-1 receptor agonist. The peptide precursor of liraglutide, produced by a process that includes expression of recombinant DNA in *Saccharomyces cerevisiae*, has been engineered to be 97% homologous to native human GLP-1 by substituting arginine for lysine at position 34. Liraglutide is made by attaching a C-16 fatty acid (palmitic acid) with a glutamic acid spacer on the remaining lysine residue at position 26 of the peptide precursor. The molecular formula of liraglutide is C₁₇₂H₂₆₅N₄₃O₅₁ and the molecular weight is 3751.2 Daltons.”

“SAXENDA injection is a sterile, aqueous, clear, colorless or almost colorless solution for subcutaneous use. Each 1 mL of SAXENDA solution contains 6 mg of liraglutide and the following inactive ingredients: disodium phosphate dihydrate, 1.42 mg; propylene glycol, 14 mg; phenol, 5.5 mg; and water for injection. SAXENDA has a pH of approximately 8.15, hydrochloric acid or sodium hydroxide may be added to adjust pH. Each prefilled pen contains a 3 mL solution of SAXENDA equivalent to 18 mg liraglutide (free-base, anhydrous).”

“Liraglutide is an acylated human glucagon-like peptide-1 (GLP-1) receptor agonist with 97% amino acid sequence homology to endogenous human GLP-1(7-37). Like endogenous GLP-1, liraglutide binds to and activates the GLP-1 receptor, a cell-surface receptor coupled to adenylyl cyclase

Abbreviated Title: Liraglutide in Teens Post-SG

Version Date: 1/30/23

activation through the stimulatory G-protein, Gs. Endogenous GLP-1 has a half-life of 1.5-2 minutes due to degradation by the ubiquitous endogenous enzymes, dipeptidyl peptidase 4 (DPP-4) and neutral endopeptidases (NEP). Unlike native GLP-1, liraglutide is stable against metabolic degradation by both peptidases and has a plasma half-life of 13 hours after subcutaneous administration. The pharmacokinetic profile of liraglutide, which makes it suitable for once-daily administration, is a result of self-association that delays absorption, plasma protein binding, and stability against metabolic degradation by DPP-4 and NEP.”

Pharmacokinetics

“Absorption -Following subcutaneous administration, maximum concentrations of liraglutide are achieved at 11 hours post dosing. The average liraglutide steady state concentration (AUC_{τ/24}) reached approximately 116 ng/mL in obese (BMI 30-40 kg/m²) subjects following administration of SAXENDA. Liraglutide exposure increased proportionally in the dose range of 0.6 mg to 3 mg. The intra-subject coefficient of variation for liraglutide AUC was 11% following single dose administration. Liraglutide exposures were considered similar among three subcutaneous injection sites (upper arm, abdomen, and thigh). Absolute bioavailability of liraglutide following subcutaneous administration is approximately 55%.

“Distribution -The mean apparent volume of distribution after subcutaneous administration of liraglutide 3 mg is 20-25 L (for a person weighing approximately 100 kg). The mean volume of distribution after intravenous administration of liraglutide is 0.07 L/kg. Liraglutide is extensively bound to plasma protein (greater than 98%).

“Metabolism -During the initial 24 hours following administration of a single [3H]-liraglutide dose to healthy subjects, the major component in plasma was intact liraglutide. Liraglutide is endogenously metabolized in a similar manner to large proteins without a specific organ as a major route of elimination.

“Elimination -Following a [3H]-liraglutide dose, intact liraglutide was not detected in urine or feces. Only a minor part of the administered radioactivity was excreted as liraglutide-related metabolites in urine or feces (6% and 5%, respectively). The majority of urine and feces radioactivity was excreted during the first 6-8 days. The mean apparent clearance following subcutaneous administration of a single dose of liraglutide is approximately 0.9-1.4 L/h with an elimination half-life of approximately 13 hours, making liraglutide suitable for once daily administration.”

Liraglutide solution (6 mg/mL, 3 ml) for subcutaneous injection via a pre-filled, multi-dose pen that delivers doses of 0.6 mg, 1.2mg, 1.8 mg, 2.4 mg, and 3.0 mg will be used within the approved dosing regimens. Table 1 illustrates the titration schedule for the drug. The study intervention is commercially available and will be purchased. The intervention dose of 3.0 mg daily is approved by the FDA to treat children 12 years and older with body weight above 60 kg and an initial BMI ≥ 30 kg/m² (or above the International Obesity Task Force BMI Cut-offs for Obesity by Sex and Age for Pediatric Patients Aged 12 Years and Older) as an adjunct to a reduced-calorie diet and increased physical activity.

There will be no IND obtained for the use of any of the commercial agents used in this study. This study meets the criteria for exemption for an IND as this investigation is not intended to support a new indication for use or any other significant change to the labeling; the drugs are already approved and marketed and the investigation is not intended to support a significant

Abbreviated Title: Liraglutide in Teens Post-SG

Version Date: 1/30/23

change in advertising; and the investigation does not involve a route of administration or dosage level in use in a patient population or other factor that significantly increases the risks (or decreases the acceptability of the risks) associated with the use of the drug product.

We have received an IND exemption for the use of liraglutide (Saxenda®) in this study. The letter documenting this exemption has been supplied to the IRB.

1.17.2 Dosing and Administration

1.17.2.1 Dose Escalation

Table 1: Titration Schedule for Liraglutide

Study schedule	Week	Liraglutide (subcutaneous injection)
Screening	-1 to 0	-
Baseline visit	0-1	0.6 mg once daily as tolerated
	1-2	1.2 mg once daily as tolerated
	2-3	1.8 mg once daily as tolerated
	3-4	2.4 mg once daily as tolerated
Target study dose	4-16	3.0 mg once daily as tolerated

The participant will start the study drug at Visit 1 (Baseline Visit) after the History & Physical Examination. The study drug will be titrated to the highest tolerable dose as per Table 1 above.

1.17.2.2 Dose Limiting Toxicity

Adverse reactions occurring in $\geq 3\%$ of SAXENDA-treated pediatric patients and more frequent than placebo are outlined in the Table below, from the package insert [61]:

	Placebo (N=126) %	SAXENDA (N=125) %
Nausea	14.3	42.4
Vomiting	4.0	34.4
Diarrhea	14.3	22.4
Hypoglycemia	4.0	15.2

Abbreviated Title: Liraglutide in Teens Post-SG

Version Date: 1/30/23

Gastroenteritis	4.8	12.8
Dizziness	3.2	10.4
Pyrexia	7.1	8.0
Abdominal Discomfort	0.8	4.8
Constipation	2.4	4.8
Dyslipidemia	3.2	4.8
Fatigue	3.2	4.8
Cough	3.2	4.0
Depression	2.4	4.0
Dyspepsia	2.4	4.0
Pain in extremity	2.4	4.0
Injection site pain	3.2	3.2
Flatulence	0	3.2
Increased Blood Creatine Kinase	2.4	3.2
Increased Lipase	0.8	3.2
Rash	0	3.2

Participants on liraglutide may experience gastrointestinal side effects like nausea, diarrhea, vomiting, decreased appetite, indigestion, and constipation. Should a participant find these side effect intolerable, their dose will not be escalated (and may be decreased) according to tolerability as described below. In addition to tolerability, dose limiting toxicities are defined in the attached Excel file titled “CTCAE_v5.0_2017-11-27 for Liraglutide.” In order to be dose limiting, the AE must be considered to be at least possibly due to the study drug.

1.17.2.3 Dose Modifications

If intolerable symptoms persist after 3 days at any dose, the liraglutide dosage will be decreased by 0.6 mg daily. If the highest tolerable liraglutide dose is less than 0.6 mg daily, the study drug will be discontinued, but the participant will be asked to return for Study Visit 5.

If gastrointestinal symptoms resolve, then at the discretion of the PI, the dose of liraglutide may be increased after 3 days to the previous dose. If participant redevelops GI symptoms on previous dose, then they should continue the max tolerated dose for the remainder of the study.

Abbreviated Title: Liraglutide in Teens Post-SG

Version Date: 1/30/23

If a dose of liraglutide is missed, the study participants will be asked to resume the once daily regimen as prescribed with the next scheduled dose. They will be instructed not to administer an extra dose or increase the dose to make up for the missed dose.

1.17.2.4 Drug Administration

Prior to first use, Saxenda will be stored in a refrigerator between 36 to 46 degrees Fahrenheit as recommended on its package insert. Participants or their parent will administer first dose of study drug (0.6 mg) subcutaneously at Visit 1 after receiving training from our research team on proper injection technique. They will also be given a medication guide (see document titled, “Saxenda for patients.” Subsequent subcutaneous doses will be administered at participants’ home daily at a consistent time. After first use of the Saxenda pen, the pen will be stored at controlled room temperature (59 to 86 degrees Fahrenheit) or in a refrigerator (36 to 46 degrees Fahrenheit) with the pen cap on.

If a dose is missed, the participant should make up the missed dose on the same day as soon as they remember and take their next daily dose as usual on the following day. The participant should not take an extra dose of the drug or increase their dose on the following day to make up for the missed dose. Any missed doses will be recorded in a patient log.

Participants will call the research team if they miss their dose of study drug for 3 days or more.

The study drug dose will be up-titrated as show in Table 1.

1.18 PREPARATION/HANDLING/STORAGE/ACCOUNTABILITY

Liraglutide (Brand name Saxenda) will be purchased from Novo Nordisk and stored in the NIH Clinical Center Pharmacy in its original packaging for use as specified in the Package Insert. The NIH Clinical Center Pharmacy will dispense the study medication per study schedule. Study medication will be supplied in 30 days’ supply at Visit 1-4.

1.18.1 Acquisition and Accountability

The study drug will be acquired and stored by the NIH Clinical Center Pharmacy. The investigator’s team will pick up the study drug from the NIH CC Pharmacy at each study visit. There is no control product in this open label trial. Empty pens will be returned at Visits 2-5 and discharged by the investigator’s team. The storage of medications will be according to the package insert for the study drug.

1.18.2 Formulation, Appearance, Packaging, and Labeling

Saxenda® solution (6 mg/mL, 3 ml) purchased from Novo Nordisk for subcutaneous injection via a pre-filled, multi-dose pen will be supplied. The solution is clear and colorless.

Participants will be requested to return all used pens as well as any expired or unused medication to Study Investigators, who will count used and unused pens and give them to the NIH pharmacy for disposal.

1.18.3 Product Storage and Stability

Prior to first use, Saxenda® should be stored in a refrigerator between 36 degrees Fahrenheit to 46 degrees Fahrenheit. After initial use of the Saxenda® pen, the pen can be stored for 30 days at controlled room temperature (59F to 86F) or in a refrigerator (36F to 46F). The pen cap

Abbreviated Title: Liraglutide in Teens Post-SG

Version Date: 1/30/23

should be kept on when not in use. Saxenda® should be protected from excessive heat and sunlight. The needle should be always removed and safely discarded after each injection [42].

1.18.4 Preparation

No preparation by study staff and/or study participants is required.

1.19 MEASURES TO MINIMIZE BIAS: RANDOMIZATION AND BLINDING

Not applicable as this is an open-label pilot study.

1.20 STUDY INTERVENTION COMPLIANCE

Administration of study intervention will be observed at Visit 1. Subsequent administration of study intervention will be verified by inspecting drug supply at Visits 2-5. One-month supply of medication will be dispensed by the NIH pharmacy at Visits 1-4. At each visit, participants will be instructed to return all used and unused study medication. The study team will count/record the number of unused pens as a measure of medication adherence.

1.21 CONCOMITANT THERAPY

For this protocol, a prescription medication is defined as a medication that can be prescribed only by a properly authorized/licensed clinician. Medications to be reported in the Case Report Form (CRF) are concomitant prescription medications, over-the-counter medications, and supplements.

Participants will be allowed to continue home medications (prescription medications, over-the-counter medications, and supplements) as long as they are not insulin, sulfonylurea, DPPIV-inhibitor or weight loss medications such as phentermine, topiramate, lisdexamfetamine, orlistat, and naltrexone HCl/bupropion HCl. All home medications and supplements will be recorded at screening and each study visit.

Liraglutide slows gastric emptying and thereby has the potential to impact the absorption of concomitantly administered oral medications. Thus, caution should be exercised when oral medications are concomitantly administered with liraglutide [42] and participants will be recommended to take their oral medications separate from liraglutide if possible.

STUDY INTERVENTION DISCONTINUATION AND PARTICIPANT DISCONTINUATION/WITHDRAWAL

1.22 DISCONTINUATION OF STUDY INTERVENTION

Discontinuation from liraglutide does not mean discontinuation from the study, and remaining study procedures should be completed as indicated by the study protocol. If a clinically significant finding is identified after enrollment (including, but not limited to changes from baseline), the investigator or qualified designee will determine if any change in participant management is needed. Any new clinically relevant finding will be reported as an adverse event (AE).

Abbreviated Title: Liraglutide in Teens Post-SG

Version Date: 1/30/23

The data to be collected at the time of study intervention discontinuation will include the following:

- History and physical
- Bloodwork per investigator discretion
- The specific underlying reason for discontinuation of study intervention or participant discontinuation/withdrawal

Participants are free to withdraw from participation in the study intervention at any time upon request. Study medication can be discontinued abruptly without untoward effects from medication withdrawal.

An investigator may discontinue or withdraw a participant from the study for the following reasons:

- Completion of study intervention
- If any clinical adverse event (AE), laboratory abnormality, or other medical condition or situation occurs such that continued participation in the study would not be in the best interest of the participant
- Investigator discretion
- Positive pregnancy test or intention of becoming pregnant
- Participant unable to receive Liraglutide for 1 week or more
- Initiation of obesity or diabetes medications or obesity treatments not permitted during the trial

1.23 PARTICIPANT DISCONTINUATION/WITHDRAWAL FROM THE STUDY

Prior to removal from study for adverse events, efforts will be made to have all subjects complete a safety visit approximately 14 days following the last dose of study therapy and to have them return at the scheduled time for Study Visit 5.

Participants are free to withdraw from participation in the study at any time upon request.

An investigator may discontinue or withdraw a participant from the study for the following reasons:

- Significant study intervention non-compliance
- If the participant meets an exclusion criterion (either newly developed or not previously recognized) that precludes further study participation
- Subject has completed the study follow-up period
- Death
- Screen Failure

The reason for participant discontinuation or withdrawal from the study will be recorded on the Withdrawal Case Report Form (CRF). Subjects will be excluded if they have any verified abnormality in laboratory values or physical status that cannot be explained by a mild intercurrent illness (or by obesity and insulin resistance itself) that in general are considered

Abbreviated Title: Liraglutide in Teens Post-SG

Version Date: 1/30/23

CTCAE 5 grade 3 or greater [62]. Problem-specific stopping rules by CTCAE5 category will be prepared in conjunction with this protocol.

Subjects who sign the informed consent form and are scheduled to be treated but do not receive the study intervention may be replaced. Subjects who sign the informed consent form and receive the study intervention, and subsequently withdraw, or are withdrawn or discontinued from the study will not be replaced.

Investigator error leading to initiation of treatment in an ineligible subject will lead to treatment discontinuation as soon as the error is uncovered. Should discontinuation be required for any reason, no tapering of liraglutide is necessary; subjects will be requested to return all unused medication.

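### Section 1.23 allows withdrawal from the study for drug non-compliance with no request to return for Visit 5, so a few week-16 values, mainly fat mass, could be lost for a reason tied to drug exposure

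*Combined protocol and SAP*

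**What the plan says.** All references are to the combined protocol and SAP, using the section numbers in its body.

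- **1.23 (withdrawal from the study)** gives the investigator discretion to withdraw a participant for, among other things, "Significant study intervention non-compliance". No return visit is attached to that ground.
- **1.22 (discontinuation of study intervention)** opens with the opposite principle: "Discontinuation from liraglutide does not mean discontinuation from the study, and remaining study procedures should be completed". Its list of reasons is nevertheless introduced by "An investigator may discontinue or withdraw a participant from the study for the following reasons", the same lead-in as in 1.23. The list includes "Participant unable to receive Liraglutide for 1 week or more" and "Initiation of obesity or diabetes medications or obesity treatments not permitted during the trial".
- **Visit 5 is requested in two situations.** In 1.23: "Prior to removal from study for adverse events, efforts will be made to have all subjects complete a safety visit", and to bring them back for Visit 5. In 1.17.2.3, a participant who cannot tolerate 0.6 mg stops drug but is asked to return for Visit 5.
- **Measurements.** Height and weight are taken at every visit (1.3, 1.26.1), and a history and physical is among the data collected when drug stops (1.22). DXA is done at Visits 1 and 5 only (1.26.1).
- **Analysis.** Secondary endpoints, including fat mass, are analysed in the ITT dataset with LOCF and a BOCF sensitivity analysis (1.33.3). The primary effect size uses the observed mean change in BMI and its SD, with no dataset or missing-data rule named for that calculation (1.33.2).
- **Replacement.** Treated participants who are withdrawn are not replaced (1.23).

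**The concern.** Stopping a drug and stopping follow-up are different events. Section 1.22 draws that line correctly, and 1.23 then allows it to be crossed for people who do not take the drug. A participant withdrawn on that ground has no week-16 value, and the reason is related to drug exposure, so the loss cannot be presumed random.

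The analysis gains nothing from such a withdrawal. Non-compliance is already handled by the Per Protocol dataset (1.32), while the ITT dataset is defined regardless of treatment received and needs the week-16 values.

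Fat mass is most exposed. With no DXA between Visits 1 and 5, carrying the last observation forward means carrying the baseline forward. The BOCF sensitivity analysis then returns the same number, so the planned check cannot show how much the imputation matters. For BMI, what could be at stake is the effect size that sizes the later randomised trial.

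**Working it through.** **Step 1. Reproduce the plan's figures.** Inputs from 1.31 and 1.33.2: liraglutide change −1.39 kg/m², placebo change +0.19, SD 3.46, one-sided α = 0.05, power 0.80. Method: noncentral t.

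- Pilot: dz = 1.39/3.46 = 0.4017. Power at n = 40 is 0.803, and 40 is the smallest n reaching 80%. The plan's 40 reproduces.
- Later trial: d = (1.39 + 0.19)/3.46 = 0.4566, giving 60 per group. The plan's 120 reproduces.

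**Step 2. How many could be lost?** The documents give no rate for withdrawal on non-compliance. Section 1.31 reports that 119 of 125 in the cited adolescent trial were still on treatment at week 16. So 6/125 = 4.8% were off treatment for any reason, and 0.048 × 43 = 2.06. Because that count covers every reason, I take it as an upper-end proxy and use an assumed range of 0 to 2 of 43.

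**Step 3. BMI, if the missing values are simply dropped.** Assume a true mean of −1.39 in all 43, and that each lost participant either had no change or lost twice the mean (−2.78).

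- SE of the pilot mean = 3.46/√43 = 0.528.
- Size of the observed mean loss with k lost = (43 × 1.39 − k × x)/(43 − k), where x is 0 or 2.78.
- d for the later trial = (observed mean loss + 0.19)/3.46.

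| Lost | Change in those lost | Observed mean | Shift as % of SE | d | Later-trial total |
|---|---|---|---|---|---|
| 0 | – | −1.39 | 0 | 0.4566 | 120 |
| 1 | 0 | −1.423 | 6.3 | 0.4662 | 116 |
| 1 | −2.78 | −1.357 | 6.3 | 0.4471 | 126 |
| 2 | 0 | −1.458 | 12.9 | 0.4762 | 112 |
| 2 | −2.78 | −1.322 | 12.9 | 0.4371 | 132 |

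For scale, move the pilot mean by one SE. At −0.862, d = 0.304 and the total is 270. At −1.918, d = 0.609 and the total is 70. Sampling error is much larger than anything in the table. Pilot power falls only from 0.828 (n = 43) to 0.811 (n = 41).

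**Step 4. Fat mass under LOCF.** A participant without a Visit 5 scan contributes zero change. If that person would have had the average change, the ITT mean shrinks by k/43: 1/43 = 2.3% for one and 2/43 = 4.7% for two. If their change off drug would have been nearer zero, the imputed zero is nearer the truth and the shrinkage is smaller. BOCF gives the same result.

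**Step 5. Does Step 3 apply to the primary?** Only conditionally. Section 1.33.2 mentions the Per Protocol dataset (at least 80% of drug on 80% of days) as one way to state the primary outcome, and names no dataset for the effect size. If the effect size is computed per protocol, a significant non-complier is likely to be excluded whether or not they attend Visit 5, and Step 3 does not arise. If it is computed on everyone with a week-16 value, Step 3 applies.

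**The case against.** The strongest reply is that the plan already protects follow-up and that little is lost.

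- **Section 1.22 covers people who stop drug.** This stands. A reader might infer from the shared lead-in that a week without liraglutide, or starting a non-permitted treatment, also takes a participant out of the study. The documents do not support that. The section is about stopping drug, its opening rule keeps remaining procedures (which include Visit 5) in place, and its first listed reason, completing the intervention, cannot mean leaving the study because Visit 6 follows off drug. What is left in 1.22 is a conflicting lead-in, a wording matter.
- **The 1.23 ground is permissive.** It says may, it is limited to significant non-compliance, and it shares a list with death, screen failure and completion of follow-up. It could be read as a catalogue of reasons for ending participation. That makes loss possible rather than certain. It does not remove the ground, which sits under withdrawal from the study and has no return visit.
- **BMI is largely protected.** This stands. Visit measurements, and the physical introduced by "The data to be collected at the time of study intervention discontinuation will include the following", normally supply a BMI near the date drug stops, and the secondary BMI analysis uses LOCF with BOCF as a check.
- **A BMI taken after another obesity treatment starts mixes two effects.** That is a fair choice of estimand. Collecting the value does not oblige the analysis to use it, whereas a visit not held cannot be recovered.
- **The fat-mass figure depends on an assumption.** This also stands. People selected for low exposure may have had less than the average change. Section 1.31 also claims no adequate power for secondary outcomes.

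**Conclusion.** The point holds for the non-compliance ground in 1.23 and is of low severity. If that ground is used, week-16 data are lost for a reason related to drug exposure. Fat mass bears most of the loss, because both the main imputation and its sensitivity check default to zero change.

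The size is small and, for BMI, of unknown direction: at most about 13% of one SE, under an assumed 0 to 2 losses of 43 and changes between zero and twice the mean in those lost. For fat mass it is 2.3% of the ITT mean change per person lost who would have had the average change, and less if their change was nearer zero.

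A reader might infer that the primary effect size, and so the size of the later trial, is biased. The documents do not establish this: 1.33.2 leaves the dataset open, and even on the exposed reading the later-trial total moves only between 112 and 132, against 70 to 270 from one SE of sampling error. This is an inexpensive improvement to follow-up and does not threaten the study's validity.

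**What to change.** 1. In 1.23, make non-compliance a reason to stop study drug only.
2. State once that every treated participant is asked back for Visit 5 whatever their drug status, with height and weight at least and DXA where feasible. The exceptions are withdrawal of consent, death, loss to follow-up, pregnancy (1.28.8), permanent loss of capacity (1.34.3), or where attending would be unsafe or not in the participant's best interest. Leave the 1.22 ground for cases where "continued participation in the study would not be in the best interest of the participant" as it is.
3. As a wording correction, change the 1.22 lead-in for a week or more without liraglutide, and for starting a non-permitted treatment, so that it refers to discontinuing study drug and agrees with that section's opening rule.

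The cost is a minor amendment, which needs IRB review and approval, and the effort of recalling a few off-drug participants to a visit already in the schedule.
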